6.6.6 Clinical Significance

Changes in laboratory values and vital signs are only considered to be AEs if they are judged to be clinically significant (ie, if some intervention or therapy is required or if the Investigator judges the change to be beyond the expected variation). Any changes or abnormalities will be considered clinically significant unless the Investigator indicates not clinically significant directly on the laboratory paperwork, eCRF or source documentation.

6.6.7 Serious Adverse Events

6.6.7.1 Definition

An SAE is defined by the Investigator or sponsor as any AE occurring during an investigational study that result in any of the following outcomes:

- Death
- Life-threatening AE

- Hospitalization or prolongation of existing hospitalization
- A persistent or significant disability (substantial disruption of the ability to conduct normal life functions)/incapacity
- A congenital anomaly/birth defect
- Important medical events that may not result in death, may be life threatening, or may require hospitalization may be considered an SAE when, based upon appropriate medical judgment, they may jeopardize the subject and may require medical or surgical intervention to prevent one of the outcomes listed in this definition. Examples of such medical events include allergic bronchospasm requiring intensive treatment in an emergency room or at home, blood dyscrasias or convulsions that do not result in subject hospitalization, or the development of drug dependency or drug abuse.

Research subjects will be instructed to notify the research center for any emergent condition and will be given the emergency contact number for the study during the consenting process.

6.6.7.2 *Expectedness*

SAEs must be assessed as to whether they were expected to occur or unexpected, meaning not anticipated based on current knowledge about the investigational compound found in the protocol or Investigator Brochure (IB) for CTAP101 Capsules, IR calcifediol, Cholecalciferol, or Paricalcitol. Categories are:

- **Unexpected** - nature or severity of the event is not consistent with the product information;
- **Expected** - event is known based on the product information.

6.6.7.3 *Reporting Serious Adverse Events*

Any AE considered serious (see [Section 6.6.7 Serious Adverse Events](#)) by the Investigator that meets the previously mentioned criteria must be reported to the following numbers within 24 hours from the time when site personnel first learn about the event.

SAE Fax line: [PPD](#)

SAE email: [contact]

A written report will follow as soon as possible and should consist of the SAE report and other necessary source documents. If the subject is hospitalized because of or during the course of an SAE, then the Investigator should attempt to obtain a copy of the hospital discharge summary and any pertinent laboratory or diagnostic reports, and provide them to the sponsor or designee as soon as possible.

For any information not available at the time of the first report that becomes available later, the Investigator should add this information to both the source documentation and the initial SAE section of the eCRFs, and provide any additional written documentation to the above number immediately or within 1 working day of receipt.

The sponsor or designee will notify the appropriate regulatory agencies of any serious and unexpected SAEs associated with the use of the investigational study drug according to regulations. Copies of any reports to regulatory agencies regarding serious and unexpected

SAEs will be provided to the Investigators by the sponsor or designee for review and submission to the IRB/EC.

If using a local IRB/EC, the Investigator is responsible for informing his or her IRB/EC per its requirements of any SAEs at that site. Copies of SAE correspondence with the IRB/EC, regulatory authorities, and other physicians must be provided to the sponsor's Clinical Services Department.

A subject experiencing one or more SAEs will receive treatment and follow-up evaluations by the Investigator, or they will be referred to another appropriate physician for treatment and follow-up. Withdrawal from the study and all therapeutic measures will be at the discretion of the Investigator at the site.

All SAEs will be followed until resolution or should the event become indistinguishable from the chronic disease condition, the subject will be followed for a minimum of 30 days after investigational study drug administration and subsequently all events will be closed. Pregnancies will be followed until six weeks following delivery to determine the outcome.

6.6.8 Treatment-Emergent Adverse Events

A TEAE is defined as any AE with onset or worsening reported by a subject from the time that the first dose of study drug is taken in this study until 30 days following discontinuation of study drug administration.

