5.2 Dosing Plan

Approximately 80 subjects will be randomized 1:1:1:1 (approximately 20 per arm) to receive one of the listed study medications with a sufficient quantity of a non-alcoholic beverage to enable swallowing of the capsules:

- 1) CTAP101 Capsules 60 mcg once daily outside of the phase 1 unit at bedtime, except on Days 1 and 29 when dosing will occur in the phase 1 unit in the morning before breakfast.
- 2) IR calcifediol 266 mcg in the phase 1 unit before breakfast on the mornings of Day 1 and Day 29.
- 3) Cholecalciferol 300,000 IU (high-dose) in the phase 1 unit before breakfast on the mornings of Day 1 and Day 29.

4) Paricalcitol 1 mcg plus cholecalciferol 800 IU (low-dose) once daily outside of the phase 1 unit in the morning before breakfast, except on Days 1 and 29 when dosing will occur in the phase 1 unit before breakfast.

After 4 weeks of treatment, subjects who are receiving paricalcitol will double the dose to 2 mcg plus cholecalciferol 800 IU once daily in the morning before breakfast provided that (a) the plasma iPTH has not decreased by at least 30% from pretreatment BL and remains above 70 pg/mL, (b) corrected serum calcium is <9.8 mg/dL, and (c) serum phosphorus is <5.5 mg/dL. Subjects who are receiving CTAP101 Capsules, IR calcifediol or cholecalciferol (300,000 IU) will not undergo upward dose titration.

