5.3 Dose Reduction Criteria

Subjects will reduce the dose of medication at any time by the schedule below in the event that plasma iPTH is confirmed to be <30 pg/mL, corrected serum calcium is confirmed to be >10.3 mg/dL, or serum phosphorus is confirmed to be >5.5 mg/dL. Subjects will suspend dosing if plasma iPTH is confirmed to be <15 pg/mL or corrected serum calcium is confirmed to be >11.0 mg/dL, and will resume when plasma iPTH is \geq 30 pg/mL and corrected serum calcium is <9.8 mg/dL per the dose schedule below.

Dose reduction:

CTAP101: decrease to 30 mcg per day (from 60 mcg per day)

IR calcifediol: hold Day 29 dose

Cholecalciferol 300,000 IU: hold Day 29 dose

Paricalcitol: decrease dose to 1 mcg per day (from 2 mcg per day).

Cholecalciferol 800 IU will not be adjusted during the study period

In the event that a dose reduction is required for a subject receiving the minimum dosage of CTAP101 Capsules (30 mcg per day) or paricalcitol (1 mcg per day), the subject will suspend dosing and resume when iPTH is \geq 30 pg/mL and corrected serum calcium is <9.8 mg/dL at the same minimum dosage.

Dose resumption:

CTAP101: 30 mcg per day

Paricalcitol: 1 mcg per day

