5.2 Pharmacokinetic properties

Vitamin D

Sun exposure: UVB light converts 7-dehydrocholesterol, found in the skin, to colecalciferol.

Absorption: Vitamin D is easily absorbed in the small intestine. Food intake potentially increases the absorption of vitamin D.

Distribution and biotransformation: Colecalciferol and its metabolites circulate in the blood bound to a specific globulin. Colecalciferol is converted in the liver by hydroxylation to 25-hydroxycholecalciferol. It is then further converted in the kidneys to 1,25-dihydroxycholecalciferol. 1,25-dihydroxycholecalciferol is the active metabolite responsible for increasing calcium absorption. Vitamin D, which is not metabolised, is stored in adipose and muscle tissues.

After a single oral dose of colecalciferol, the maximum serum concentrations of the primary storage form are reached after approximately 7 days. 25(OH)D₃ is then slowly eliminated with an apparent half-life in serum of about 50 days. Colecalciferol and its metabolites are excreted mainly in the bile and faeces.

Elimination: Vitamin D is excreted mainly in bile and faeces with a small percentage found in urine.

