## 9 SAFETY ANALYSIS

### 9.1 Adverse Events

Adverse events will be coded using MedDRA (Version 21.0 or higher). Each verbatim term will be mapped to a SOC and PT. Severity grades for safety parameters will be assigned using the Common Terminology Criteria for Adverse Events (Version 5.0). When changes in the severity of an AE occur more frequently than once a day, the maximum severity for the experience that day will be noted.

Treatment-emergent AEs (TEAE) are events with onset dates and times on or after the administration of the first dose of study drug and within 30 days after the last dose of study drug, or a continuing AE diagnosed before the date of the first dose of study drug, which increases in frequency, severity, or character during the course of the study.

An overall summary of TEAEs will be provided for the safety population summarizing subjects with at least 1: TEAE, related TEAE, grade 3, 4, or 5 TEAE, serious TEAE, related serious TEAE, TEAE leading to study discontinuation, or related TEAE leading to study discontinuation as well as the number of events within each of the previously mentioned categories by treatment.

In addition, summaries of unique TEAEs will be presented for the safety population by SOC, PT, and by treatment and overall, and will include the number and percentage of subjects who experience the unique event for:

1. All TEAEs,
2. All TEAEs by relationship,
3. All TEAEs by severity grade,
4. All TEAEs leading to study discontinuation,
5. All serious TEAEs, if more than 1 serious TEAE is recorded.

Related TEAEs include all those classified by the investigator as possibly related or related. Unrelated TEAEs are those events classified as not related or unlikely related.

For summaries by relationship, the most related event will be selected. For summaries by severity, the most severe grade will be selected.

Multiple events will be counted only once per subject and treatment in each of the previously mentioned summaries by treatment and overall. In the presentation, SOC and PT will be sorted in alphabetical order.

All AEs captured in the database will be presented in by-subject data listings; however, only TEAEs will be summarized.

MedDRA version will be provided in a footnote in both tables and data listings.

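### Under SAP 9.1, a monthly-arm subject whose Day 29 dose is held can contribute no new-onset TEAE after Day 31, although follow-up runs to Day 57

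*Protocol*

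**What the plan says.** **TEAE window.** Protocol 6.6.8 takes onset or worsening from the first dose "until 30 days following discontinuation of study drug administration". SAP 9.1 takes onset from the first dose and "within 30 days after the last dose of study drug". The SAP has a second limb for an AE that was present before the first dose and "which increases in frequency, severity, or character during the course of the study". That limb carries no 30-day limit.

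**What is tabulated.** Protocol 6.6.3 has all AEs after consent recorded. SAP 9.1 puts them all in by-subject listings; "however, only TEAEs will be summarized".

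**Dosing in the monthly arms.** Protocol 5.2 gives "IR calcifediol 266 mcg in the phase 1 unit before breakfast on the mornings of Day 1 and Day 29" and "Cholecalciferol 300,000 IU (high-dose) in the phase 1 unit before breakfast on the mornings of Day 1 and Day 29".

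**Dose reduction.** Under Protocol 5.3 the triggers are confirmed iPTH below 30 pg/mL, corrected calcium above 10.3 mg/dL or phosphorus above 5.5 mg/dL. The action in the first monthly arm is "IR calcifediol: hold Day 29 dose", and the high-dose cholecalciferol arm has the same instruction. CTAP101 goes from 60 to 30 mcg per day. The resumption schedule (Protocol 5.3, SAP 3.3) names only CTAP101 and paricalcitol.

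**Follow-up.** A held dose is not in itself a withdrawal reason in Protocol 6.8. AE assessments continue on Days 36, 43, 50 and 57 (Protocol 7.2.6, 7.3.1 and Appendix 1).

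**The concern.** A window tied to the last dose works when dosing stops near the end of follow-up. In a monthly regimen with two planned doses, a single held dose moves the last dose back by four weeks and takes the TEAE window with it. Neither document makes an exception for this case.

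The subjects affected are not a random subset, because their dose was held after they met a safety threshold. A CTAP101 subject who meets the same threshold at 60 mcg and is reduced to 30 mcg keeps dosing and is counted to Day 57. The same laboratory finding can therefore lead to different lengths of tabulated AE follow-up, depending on the arm. AEs are among the primary safety endpoints (Protocol 2.2.3), and comparing safety across the four regimens is a principal aim (Protocol 3.2).

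The differing wording of the two definitions adds a second problem. The same late event may be a TEAE under one document and not under the other.

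**Working it through.** **Inputs**
- Monthly doses on Days 1 and 29: Protocol 5.2.
- Last visit on Day 57: Protocol 7.3.1.
- Daily regimens run for 56 days: SAP 3.3.
- Window of 30 days after the last dose: SAP 9.1.
- About 20 subjects per arm, so about 40 in the two monthly arms: Protocol 3.1.
- Calcifediol half-life of 18 to 21 days: product information in Protocol Appendix 2, section 5.2.
- After cholecalciferol, a 25(OH)D3 "apparent half-life in serum of about 50 days", with the peak at about 7 days: product information in Protocol Appendix 4, section 5.2.

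**Day count.** SAP 7.2 places the Day 57 sample 28 days after the Day 29 dose. 29 + 28 = 57, so the convention reproduces.

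**Window close under SAP 9.1.** Close = last-dose day + 30. On-study days outside = max(0, 57 − close).

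| Subject | Last dose | Window closes | On-study days outside |
|---|---|---|---|
| Monthly arm, both doses | Day 29 | Day 59 | 0 |
| Monthly arm, Day 29 held | Day 1 | Day 31 | 57 − 31 = 26 |
| Daily arm, dosed to Day 56 | Day 56 | Day 86 | 0 |

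For the held-dose subject the excluded days are 32 to 57: 26/57 = 45.6% of study days. They contain four scheduled AE assessments (Days 36, 43, 50 and 57). For any subject, the window reaches Day 57 only if the last dose falls on Day 57 − 30 = Day 27 or later.

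**Protocol 6.6.8.** If discontinuation is dated to the hold on Day 29, the window closes on 29 + 30 = Day 59 and no on-study day is lost. If it is dated to the last dose taken, it closes on Day 31. The text does not say which applies.

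**Exposure at the cutoff.** The share remaining 30 days after the Day 1 dose is 0.5^(30/half-life).
- IR calcifediol: 0.5^(30/18) = 0.31 and 0.5^(30/21) = 0.37.
- Cholecalciferol-derived: 0.5^(30/50) = 0.66. Counting from the peak at 7 days instead, 0.5^(23/50) = 0.73 of peak. This half-life comes from the 800 IU product's information, so its use for the 300,000 IU regimen is an assumption.

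Either way, exposure has not ended at Day 31.

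**How many subjects.** The documents give no hold rate. For an assumed rate r, affected subjects = 40r, and the share of monthly-arm study days outside the window = r × 26/57.

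| Assumed r | Subjects of 40 | Monthly-arm days outside |
|---|---|---|
| 5% | 2 | 2.3% |
| 10% | 4 | 4.6% |
| 20% | 8 | 9.1% |

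**Effect on a table row.** One subject in an arm of 20 is 1/20 = 5 percentage points, and that is the maximum.

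**With the window extended.** Close = max(57, last-dose day + 30). The held-dose subject is covered to Day 57 and loses 0 days. The other two rows of the first table do not change up to Day 57.

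**The case against.** Several stronger readings are tempting, and the documents do not support them.

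- **That the protocol itself imposes the Day 31 cutoff.** It does not do so clearly. Protocol 6.6.8 refers to discontinuation, and Protocol 5.3 classes the hold as a dose reduction. Only the SAP wording yields Day 31 directly. This objection stands, so the point rests on SAP 9.1 and on the mismatch.
- **That only the monthly arms lose follow-up.** A CTAP101 subject suspended for good before Day 27 also loses days. Paricalcitol subjects start at the minimum dose, so a trigger before Day 29 leads to suspension. Their 800 IU cholecalciferol is not adjusted, which leaves the last study-drug dose in that arm unclear. The asymmetry shown here is between a held monthly dose and a CTAP101 reduction from 60 to 30 mcg.
- **That safety data are lost.** Late AEs remain in the listings, and serious events and deaths have their own listing (SAP Appendix A, 14.3.2). The laboratory summaries (SAP 9.2) and the hypercalcemia and hyperphosphatemia counts (SAP 9.3) are not tied to the TEAE window. Worsening of a pre-dose AE still counts under the SAP. Safety analysis is descriptive (Protocol 9.10), so no safety test is affected.
- **That every held-dose subject costs 5 points.** Protocol 6.6.3 and 6.6.6 tend to make a laboratory change that prompts action an AE. Such a subject may well already have a TEAE by Day 31 and already count in the any-TEAE row. The loss then falls on rows by organ class and preferred term, severity, relationship and seriousness, and on event counts.
- **That completers are also biased, because 30 days after the last dose are never observed.** Follow-up does end before the nominal window closes, but this excludes no observed event.

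None of this removes the narrower point: on the SAP wording, collected new-onset events on Days 32 to 57 are left out of the TEAE tables for held-dose subjects.

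**Conclusion.** The point holds in this limited form. Under SAP 9.1, a monthly-arm subject with a held Day 29 dose has 26 of 57 study days and four scheduled visits outside the window for new-onset TEAEs. The subjects concerned have already met a confirmed safety trigger. Protocol 6.6.8 can be read as covering the whole period, so the two definitions need to be reconciled.

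The conclusion assumes that the last dose in SAP 9.1 means the last dose taken, that a held monthly dose is not given later, and that the subject stays on study to Day 57. The overall effect depends on a hold rate that the documents do not give. At an assumed 5% to 20%, it concerns 2 to 8 of 40 subjects, each moving any one row by at most 5 percentage points. The direction is towards fewer tabulated late events in those subjects. This is worth correcting before database lock, but it does not threaten the collected safety data or the laboratory endpoints.

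**What to change.** Use one definition in both SAP 9.1 and Protocol 6.6.8: a TEAE is an AE with onset or worsening from the first dose of study drug through the later of the EOS/ET visit and 30 days after the last dose.

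This covers held-dose subjects to Day 57, covers daily-arm subjects who stop early up to their EOS/ET visit, and changes nothing up to Day 57 for fully dosed subjects. It also removes the need to decide when a held dose counts as discontinuation.

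The cost is about one sentence in each document. SAP section 1 already provides for an amendment or addendum before database lock. No visit, data item or dosing rule changes. The downside is that a few more late AEs are counted as treatment-emergent.

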6.7 Concomitant Medication Assessments

The study coordinator or designee will record concomitant medication history in the source document and eCRF. Changes in phosphate binder and calcium supplement therapy will be collected on a separate page in the eCRFs.

6.8 Removal of Subjects from the Study or Study Drug (Early Termination)

The Investigator may withdraw a subject from the study for any of the following reasons:

- A major protocol deviation occurs;
- A serious or intolerable AE occurs;
- A clinically significant change in a laboratory parameter occurs;
- The sponsor or Investigator terminates the study;
- The subject requests to be discontinued from the study;
- If the Investigator believes it is no longer in the best interests of the subject to continue;
- A subject becomes pregnant;

No subject replacement is planned.

6.9 Appropriateness of Measurements

AEs, corrected serum calcium and serum phosphorus have been used to assess safety of vitamin D compounds and will be monitored in this study. The safety and tolerability of each study

medication will be determined by analyzing AEs, corrected serum calcium and serum phosphorus.

CCI

Pre and post-dose averages will be used to minimize the effect of any intrasubject and interassay variability.

7 STUDY ACTIVITIES

7.1 Screening Period

7.1.1 *Visit 1 (Days -70 or -42 to -36)*

- A signed ICF will be obtained from the subject prior to any study-related procedures
- Review of inclusion/exclusion criteria
- Medical history and demographics
- Review of prior and current medications
- PE (including weight, height and BMI)
- VS assessment
- Serum pregnancy test (for females of child bearing potential)
- Serum hepatitis B and C/HIV screen
- Drugs of abuse screen
- eGFR
- Urinary albumin excretion
- Blood samples will be drawn for the following:
 - Clinical chemistry (full panel) and hematology
CCI [REDACTED]
- Dietary questionnaire for calcium intake and counseling, if needed.

If the screening values do not meet study entry criteria after visit 1, subject may receive supportive care per the investigator's discretion and may be retested once. If values do not fall within study entry criteria on retest, the subject will be considered a screen failure and be withdrawn from the study. Only the screening values that did not meet entry criteria at visit 1 are required to be re-drawn and meet entry criteria at the time of the visit 1 retest.

7.1.2 *Visits 2 and 3 (Within Days -7 to -1)*

- Review of inclusion/exclusion criteria
- Review of concomitant medications
- AE assessment
- VS assessment
- Serum pregnancy test (for females of child bearing potential) (Visit 2 only)
- Blood samples will be drawn for the following:
 - Clinical chemistry (full panel) and hematology
CCI [REDACTED]
- Blood samples will be drawn for:
 - CCI [REDACTED] calcifediol, and CCI [REDACTED]
CCI [REDACTED]

CC1

- [REDACTED]
- Subjects will be instructed to report to the phase 1 unit for Visit 4 after an overnight fast.

7.2 Treatment Period

7.2.1 Visit 4 (Day 1)

Randomization will occur at the start of this visit.

- Subjects admitted into the phase 1 unit (for approximately 14 to 26 hours) after an overnight fast.
- Subjects will receive standardized meals while housed in the phase 1 unit. These meals will contain approximately 400 mg of elemental calcium and will be administered at approximately 2 (breakfast), 6 (lunch), and 10 (dinner) hours post-dose.
- Review of concomitant medications
- VS assessment
- Blood samples will be drawn from subjects housed in the phase 1 unit at approximately 6:00 a.m. ($t=$ ~2 hours), and 8:00 a.m. ($t=$ ~0 hours) and precisely (plus or minus 5 minutes, with exact time noted) at $t=$ 2, 4, 6, 12 and 24 hours (for subjects opting overnight stays), post-dose for the following analyses:
 - Chemistry (partial panel)

CC1

- Serum calcifediol, CC1
- Additional blood samples will be drawn from subjects housed in the phase 1 unit at approximately 8:00 a.m. ($t=$ ~0 hours) and precisely (plus or minus 5 minutes, with exact time noted) at $t=$ 12 and 24 hours (for subjects opting overnight stays) post-dose for the following analysis:

CC1

 - AE assessments will be completed at each timed blood draw (n=6)
 - Subjects take first dose of study drug with a sufficient quantity of a non-alcoholic beverage to enable swallowing of the capsules immediately after the $t=$ 0 blood draw, with the exact time of dosing noted.

CC1

[REDACTED]

- Subjects will be discharged from the phase 1 unit after the blood draw at 12 hours post-dose unless Subject chooses to stay overnight. Subjects opting to remain in the phase 1 unit for overnight will have 24 hour read completed. Those who do not opt to stay overnight, advance to Visit 5.
- Balance of monthly study drug supply dispensed at discharge to subjects assigned to CTAP101 Capsules and paricalcitol capsules plus low-dose cholecalciferol.

[figure not shown]
